8.7.3 Informed consent procedure

The study will be conducted in accordance with the ethical principles that have their origin in the Declaration of Helsinki. Eligible patients may only be included in the trial after written informed consent is obtained. Informed consent must be obtained prior to conducting any trial specific procedures and the process for obtaining informed consent must be documented in the participant's medical records (source documents will be reviewed at the time of on-site monitoring visits).

Informed Consent Forms (ICF) approved by the REC will be provided by the CTU. The PI or designee is responsible for ensuring that informed consent for trial participation is given by each participant prior to any trial treatment being administered. This requires that the ICF be signed and personally dated by the participant prior to any trial treatment proceeding. If no consent is given, a patient cannot be recruited into the trial.

The CTU will provide the PIL approved by the REC. The PI or designee is responsible for ensuring that all patients are given a copy of the PIL and are allowed adequate time to review this and have had the opportunity to ask any study related questions. All participants should have the capacity to self-consent; this should be judged by the PI or the designated member of the study team who will have the responsibility for taking consent. The PI (or designee) taking informed consent must be GCP trained, suitably qualified and experienced, and have been delegated this duty by the PI on the delegation log. Two copies of the ICF must be signed and personally dated by the participant and the individual taking consent. A copy of the signed ICF will be filed in the participant's medical records, whilst the originals will be retained by the participant and by the PI in the Investigator Site File (ISF).

The participant's medical notes will be annotated by the PI to confirm that the participant has provided written informed consent and has been recruited onto the study.

Following the recruitment of a participant onto the study, the PI or designee will issue a letter to the participant's GP to inform them that their patient is participating in the MIRROR trial. The participant will be advised of this contact with their GP on the REC approved PIL. If the recruited participant is not already a registered patient, a referral letter will be requested from their GP.

Surgical consent will also be sought from those participants randomly allocated to the intervention group. This is per standard NHS/Trust guidelines and will be conducted at the pre-operative visit. A full discussion of both the laser procedure, if needed, and the surgical procedure will be carried out by the operating surgeon or their designee. A copy of the surgical consent will be retained in the CRF and the participant's medical notes.

8.7.4 Withdrawal of consent

Participants may withdraw or be withdrawn from the trial at any time without prejudice. In the event of consent withdrawal, participants will be asked for their permission to use the data already collected to date. If this permission is declined, any data collected to date on that participant will not be entered into the trial analysis. A withdrawal of consent form will be completed in the CRF defining further use of data.

All study investigators will be informed of the participant's withdrawal and they will not be contacted again with regards to the study. If the participant requests removal of the OriLens device, an appointment will be provided by the operating surgeon and the participant will be given the

opportunity to discuss the request for removal. The consultation will include discussion on reason for the request to have the device removed and the potential risks and benefits of removing the device. If removal goes ahead, the participant will revert to standard care treatment.

Withdrawal of consent, participant/PI request not to proceed with implantation of the OriLens, or participant/PI request to have the OriLens removed will be recorded on the CRF.

9 Methods: Assignment of interventions

9.1 Sequence Generation

Eligible participants will be allocated to either implantation of the OriLens device with three sessions of low vision training or to standard of care with three sessions of low vision training. The randomisation will use a 1:1 allocation ratio between treatments. The randomisation will be stratified by site.

The randomisation sequence will be saved in a restricted area of the TMF which will only be able to be accessed by statisticians and not those who enrol or assign interventions.

9.2 Allocation Concealment Mechanism

The randomisation sequence will be concealed using a number of measures including:

- i) Using a central telephone randomisation service provided by NICTU
- ii) Restricting access to the randomisation sequence

9.3 Allocation Implementation

The randomisation sequence will be generated by a statistician from NICTU as per the departmental SOPs.

When the research team at each study site identifies a patient suitable for enrolment, they will obtain informed consent for participation in the trial. After laser treatment, the PI or designee will phone the central telephone randomisation service provided by NICTU to randomise the participant. The research team will notify the participant within 72 hours regarding the group to which they have been allocated.

9.4 Masking

Due to the surgical procedure, it will not be possible to mask the participants. As the device is easily visible with the naked eye due to the reflections from the mirror, it will not be possible to mask the observers however the final assessment for the primary outcome will be measured by an independent observer who will be asked not to discuss the trial with the participant (See Section 8.4.1).

10 METHODS: DATA COLLECTION, MANAGEMENT AND ANALYSIS

10.1 Data Quality

The CI and CTU will provide training to site staff on trial processes and procedures including CRF completion and data collection. Within the CTU, the clinical data management process is governed by Standard Operating Procedures (SOPs) which help ensure standardisation and adherence to ICH-GCP guidelines and regulatory requirements.

On-site monitoring visits during the trial will check the accuracy of entries on CRF, the adherence to the protocol, trial specific procedures and Good Clinical Practice (GCP). This monitoring will be carried out as per the trial specific monitoring plan. Changes to data will be recorded and fully auditable. Data errors will be documented and corrective actions implemented.

Data validation will be implemented and discrepancy reports will be generated following data entry to identify data that may be out of range, inconsistent or protocol deviations based on data validation checks programmed into the clinical trial database.

A Data Monitoring & Ethics Committee (DMEC) will be convened for the study to carry out reviews of the study data at intervals during the study.

10.2 Data Collection

10.2.1 Screening/Baseline Visit and Procedures

The screening tests will be conducted as per Section 8.7.2 above during two screening visits. The following baseline questionnaires will be administered at the end of the second screening visit:

- Health related quality of life (EQ-5D-5L)
- Vision-related quality of life (IVI)

10.2.2 Study Visits and Procedures

Pre-randomisation (Day -20 to -7) (Both groups)

Nd: YAG Capsulotomy in study eye (if not already done)

Pre-operative (Day -7 to -1) (Intervention group only)

Pre-op medical history assessment Visual acuity (distance only) and ophthalmic examination Informed consent for surgical procedure

Day 0 (Intervention group only)

Surgical procedure Standard surgical report (post-operatively)

Day 1 Post-operative (Intervention group only)

Medical history, ophthalmic examination Visual acuity (Distance only) Adverse events check

Day 7 Post-operative (Intervention group only)

Medical history, ophthalmic examination

Visual acuity (distance and near), reading speed, refraction, and contrast sensitivity Adverse events check

1 Month (approximately 6-8 weeks post randomisation) (Both groups)

Medical history, ophthalmic examination Visual Acuity (distance and near), reading speed, refraction, and contrast sensitivity Spectacle prescription dispensing and voucher for glasses Visual Rehabilitation training Adverse events check

3 months (approximately 14 weeks post randomisation) (Both groups)

Medical history, ophthalmic examination Visual Acuity (distance and near), reading speed, refraction, and contrast sensitivity Visual Rehabilitation training Adverse events check

6 months (approximately 6-7 months post randomisation) (Both groups)

Medical history, ophthalmic examination Visual Acuity (distance and near), reading speed, refraction, and contrast sensitivity Health related quality of life (EQ-5D-5L) Vision-related quality of life (IVI) Health service use questionnaire Spectacle prescription dispensing and voucher for glasses Adverse events check

12 months (approximately 12-13 months post randomisation) (Both groups)

Medical history, ophthalmic examination Visual Acuity (distance and near), reading speed, refraction, and contrast sensitivity Fundus photography Specular microscopy Health related quality of life (EQ-5D-5L) Vision-related quality of life (IVI) Health service use questionnaire Spectacle prescription dispensing Visual Rehabilitation training Adverse events check

10.3 Study Instruments

Best corrected distance visual acuity (BCDVA) will be obtained in both eyes by an optometrist trained in research studies using the ETDRS charts at screening visit one and months one, three, six and 12. Additionally, BCDVA will be obtained pre-operatively and on days one and seven post-operatively in the intervention group. BCDVA can be a variable endpoint depending on the assessor. In order to reduce variability, participants can be encouraged to read to achieve their best visual acuity. Furthermore, an additional independent assessor will repeat the BCDVA at the 12-month time point. Refraction will be prepared by the optometrist on the research team prior to the assessment and the independent assessor will be instructed not to look directly at the participant's eyes. As an additional measure to aid masking, the trial frames will be placed on the participant by the research optometrist.

Vision-related quality of life will be measured using the IVI (18). The IVI has been validated in AMD and the subscales of IVI (reading and assessing information, mobility and independence, and

emotional well-being) have been demonstrated to have superior-quality psychometric properties and validity (22, 23). It will be administered at baseline, and six and 12 months post-randomisation.

Health related quality of life will be measured using the EQ-5D-5L (17). The EQ-5D-5L is a generic preference-based instrument which provides a description of health using five dimensions (mobility, self-care, usual activities, pain/discomfort and anxiety/depression) each with five levels of severity. Responses are converted to an overall utility score which will be used for the calculation of quality adjusted life years (QALYs). Respondents are also asked to place their health on a visual analogue scale (VAS) where 0 represents the worst imaginable health state and 100 the best imaginable health state. It is recommended by NICE (24) for use in economic evaluations. It will be administered at baseline, and six and 12 months post-randomisation.

A resource use questionnaire has been developed specifically for the MIRROR study. It will measure participants' use of health services (community, social, hospital and care services) up to 12 months post-randomisation. It will also measure participants' use of privately purchased vision aids and the costs of these. It will be administered at six and 12 months post-randomisation.

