Although the OriLens is suitable for implantation both at the time of cataract surgery and in eyes that have had previous cataract surgery, it is the opinion of the investigators that the best trial design is to carry out the study in eyes that have had previous cataract surgery (pseudophakic eyes). The main reason for this is that a proportion of eyes which have had cataract extraction will develop posterior capsular opacification (PCO). PCO causes reduction in vision and often requires treatment by laser (neodymium-doped yttrium aluminium garnet (Nd:YAG)) capsulotomy. Nd:YAG capsulotomy is however contraindicated following OriLens implantation as laser energy could cause damage to the device. It is therefore important to avoid the need for Nd:YAG capsulotomy after OriLens implantation, thus the current study design includes a Nd:YAG capsulotomy for all participants. All participants will undergo Nd:YAG capsulotomy (unless already carried out) prior to randomisation. Nd:YAG capsulotomy is a routine procedure in many pseudophakic patients and the risk has been shown to be negligible. In a study of over 12,000 consecutive cataract surgeries, a number of factors were associated with retinal detachment post cataract surgery however Nd:YAG capsulotomy was not (12). A second and important reason in terms of efficacy, is that that cataract surgery alone will in itself give an improvement in various aspects of visual function, not just acuity, and as such removal of the cataract could be the reason for improvement in visual function. The current methodology takes this variable out of the equation.

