8.2.2 Inclusion Criteria

- Age 55 years or above
- Bilateral stable advanced AMD either neovascular (required to be stable for at least 12 months after last treatment) or atrophic AMD
- Bilateral uncomplicated cataract surgery with unifocal intraocular lenses
- Bilateral BCDVA of 6/38- 6/240 (LogMAR 0.80 to 1.60) and above
- Must demonstrate a 10-letter (0.20 LogMAR) improvement in BCDVA (ETDRS chart) with the external x2.5 telescope in the eye for implantation
- Must have had experience of using low vision aids
- Have an endothelial cell density appropriate for age as detailed in Appendix I
- Be willing to undergo laser capsulotomy in the eligible eye prior to randomisation (if required)
- Must be three months or more following any intraocular surgical or laser procedure
- Must be in good general health with every likelihood of involvement in the trial for the duration of the study and be able to physically or verbally complete the questionnaires
- Only one eye per participant will be included in the study.

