10.6.2 Statistical methods

The primary endpoint is the change from baseline of BCDVA at the 12-month time point in the study eye. The treatments will initially be compared using the independent t-test followed by a repeated measures analysis of covariance, adjusting for site, baseline BCDVA as a covariate and other covariates/factors where appropriate. Possible covariates/ factors will be discussed in the Statistical Analysis Plan (SAP) and may include size of scar, thickness of scar, and ocular dominance. Statistical diagnostic methods will be used to check for violations of the model assumptions and data transformations or non-parametric equivalents such as Mann-Whitney may be performed as appropriate. The primary data at 12 months are the BCDVA measurements by the independent assessor. The 12 month BCDVA data measured by the optometrist on the research team will be analysed as part of a sensitivity analysis.

The continuous secondary endpoints will be analysed in the same manner as the primary endpoint with an endpoint specific baseline covariate term included.

Analyses will be two-sided and tested at an a priori significance level of p=0.05. The primary time point has been defined as the 12-month time point. There is no adjustment for multiple testing at the different time points, as the primary outcome has been defined and prioritised.

For the mechanistic evaluation, descriptive statistics will be used to present the results. Also, the relationship between visual outcome and several factors (as discussed in Section 7.1) will be investigated using the independent t-test, 1-way analysis of variance, Pearson's correlation coefficient or non-parametric equivalents as appropriate depending on the scale of measurement of the factors.

Inter-rater reliability between the independent assessor and the optometrist on the research team will be tested for BCDVA at 12 months using the intra-class correlation coefficient.

Baseline characteristics, follow-up measurements and safety data will be described graphically and in tabular format using appropriate descriptive summary measures depending on the scale of measurement and distribution.

A detailed SAP will be written by the trial statistician prior to the final analysis.

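### Baseline acuity and the entry decisions based on it predate the trial's own laser capsulotomy, so 12-month change includes any laser gain; the three-month laser criterion has no reference date

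*Protocol*

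**What the plan says.** - **Endpoint.** Section 10.6.2: "The primary endpoint is the change from baseline of BCDVA at the 12-month time point in the study eye". It does not say which visit is baseline. The screening section is headed "10.2.1 Screening/Baseline Visit and Procedures", which points to screening.
- **Acuity schedule.** In both arms BCDVA is taken "using the ETDRS charts at screening visit one and months one, three, six and 12" (section 10.3). Table 2 puts Screening 1 at Day -45 to -20. The section continues: "Additionally, BCDVA will be obtained pre-operatively and on days one and seven post-operatively in the intervention group". The pre-operative visit is at Day -7 to -1.
- **Trial laser.** Sections 7.1 and 10.2.2 and Table 2 place Nd:YAG capsulotomy of the study eye at Day -20 to -7 in both arms, unless already done, and before randomisation. Section 7.1 gives the reason to expect an effect on acuity: "PCO causes reduction in vision and often requires treatment by laser".
- **Entry decisions.** The 0.80-1.60 LogMAR range, the 10-letter telescope gain (section 8.2.2) and the choice of study eye (section 8.2.4) rest on screening acuity. Section 8.5 settles all of them before the laser.
- **Three-month criterion.** Section 8.2.2: "Must be three months or more following any intraocular surgical or laser procedure". The same list requires willingness to have the trial laser before randomisation.
- **Other uses of acuity.** The mechanistic evaluation uses only participants who were randomised to the implant and received it (section 10.6.1). The safety outcomes include any reduction in visual acuity (section 8.4.2).

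**The concern.** Section 7.1 justifies enrolling pseudophakic eyes on the ground that cataract removal could itself improve vision and so obscure the effect of the device. Placing a vision-restoring laser after the only pre-treatment acuity test that both arms share lets a similar influence back in. For anyone lasered in the trial, the 12-month change is laser gain plus everything that follows.

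Randomisation balances this between arms. It does nothing for summaries within one arm. The mechanistic analysis relates visual outcome to scar, retinal locus and dominance in implanted eyes alone, so laser gain becomes an unmodelled part of the outcome. In the safety summary, a gain from the laser can hide a later loss when the reference value is pre-laser.

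The SAP can name the baseline visit. It cannot supply a post-laser, pre-treatment acuity in controls, because the schedule does not collect one.

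Separately, the three-month laser criterion states no date at which it applies and no exemption for the trial laser.

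**Working it through.** **1. The plan's own figure.** Inputs from sections 8.6 and 10.6.2: difference 8.06 letters, SD 13.4, two-sided 0.05, power 0.90, 1:1, 10% attrition.

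n = 2(1.960 + 1.282)² × 13.4² / 8.06² = 58.1, so 59 per arm. 59 / 0.90 = 65.6, so 66 per arm and 132 in total. This reproduces the protocol. Power at 59 per arm is 0.900 by the noncentral t.

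**2. Assumptions.** The protocol gives neither the share needing trial laser (p) nor the mean gain in letters (L). I take p = 0.25 to 0.75 and L = 2 to 8. Where the gain also varies between people, its SD is s.

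**3. Screening 1 as baseline in both arms.** The laser precedes randomisation, so it adds pL to the mean change in each arm:

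- Shift within each arm: 0.25 × 2 = 0.5 up to 0.75 × 8 = 6.0 letters.
- Expected difference: 8.06 + pL - pL = 8.06, unchanged.
- Chance imbalance in laser use has SD L√(p(1-p) × 2/59), from 0.16 to 0.74 letters. Randomisation is stratified by site only.

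**4. Variance and power.** Added variance = p(1-p)L² + ps², on top of 13.4² = 179.56. Power is by the noncentral t at 59 per arm.

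| p | L | s | Added variance | SD | Power |
|---|---|---|---|---|---|
| 0.25 or 0.75 | 2 | 0 | 0.75 | 13.43 | 0.90 |
| 0.5 | 2 | 0 | 1.00 | 13.44 | 0.90 |
| 0.25 or 0.75 | 5 | 0 | 4.69 | 13.57 | 0.89 |
| 0.5 | 5 | 0 | 6.25 | 13.63 | 0.89 |
| 0.25 or 0.75 | 8 | 0 | 12.00 | 13.84 | 0.88 |
| 0.5 | 8 | 0 | 16.00 | 13.98 | 0.87 |
| 0.5 | 5 | 5 | 18.75 | 14.08 | 0.87 |
| 0.5 | 8 | 6 | 34.00 | 14.61 | 0.84 |

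The normal approximation gives 0.88 to 0.90 for the first six rows, and there the number needed for 90% power is 59 to 64 per arm. A yes/no covariate for trial laser removes the p(1-p)L² part: all of the added variance when the gain is constant, 6.25 of 18.75 in the seventh row, and 16 of 34 in the last.

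**5. Pre-operative value as baseline in the implant arm only.** This case is hypothetical. The implant arm's change then excludes the laser gain and the control arm's includes it, so the expected difference is 8.06 - pL. With p = 0.5 and L = 5 it is 8.06 - 2.5 = 5.56 letters, and power is 0.61. Across the assumed range it runs from 7.56 letters (power 0.86) to 2.06 letters (power 0.13).

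**6. Laser-to-surgery interval.** By Table 2, laser at Day -20 to -7 and surgery at Day 0 are at most 20 days apart. By the text, allocation is notified within 72 hours of laser (section 8.5) and surgery follows within eight weeks of randomisation (section 8.3.1), so at most about 3 + 56 = 59 days. Both are under three months. Someone lasered in the trial can meet the criterion at screening, but not if it is applied at randomisation or surgery.

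**The case against.** The strongest reply is that the treatment comparison is protected, and it is. A reader might infer that the primary result is biased because the baseline precedes the laser. The documents do not support that: both arms are lasered before randomisation, Screening 1 is the only pre-treatment BCDVA scheduled in both, and section 10.2.1 labels screening as baseline. The protocol never calls the pre-operative value a baseline, so step 5 describes a misuse to be ruled out, not the plan.

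A reader might also infer that only the implant arm is ever tested again after the laser. Controls are tested from Month 1; the asymmetry is confined to the period between laser and Day 0.

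Nor is the three-month criterion a proven contradiction. Section 8.5 judges eligibility at the screening visits, before the laser, and the criterion can be met then. What remains is that the text gives neither a reference date nor an exemption.

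The power figures rest on assumed inputs. The exclusion for lack of a clear retinal view should limit dense opacity, and some eyes will already have been lasered. The SD of 13.4 comes from change after cataract surgery, so adding laser variance to it is itself an assumption. Adjustment for baseline BCDVA may absorb part of the effect. These points support treating the power loss as modest.

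Covariates and the baseline definition can be left to the SAP. The missing post-laser measurement in controls cannot.

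**Conclusion.** The point holds in a limited form. With a common Screening 1 baseline the between-arm difference is unbiased in expectation. The cost is that change within each arm carries a laser gain of pL (0.5 to 6.0 letters over the assumed range), which also enters the implant-only mechanistic analysis and can mask acuity loss in the safety summary. Power falls from 0.90 to between 0.87 and 0.90 with a constant gain, and to 0.84-0.87 in the two cases where the gain varies between people. Entry acuity, telescope gain and study-eye choice likewise describe the eye before the laser. All these sizes depend on assumed values of p, L and s, since the protocol supplies none.

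The three-month criterion and the trial's own laser timings are unreconciled. This review does not say which governs.

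**What to change.** 1. State that Screening 1 is the baseline for the primary analysis in both arms, and that the pre-operative value is never used for it. This costs one sentence.
2. Add capsulotomy done in the trial (yes/no) to the primary model. It is fixed before randomisation, so adjusting for it is safe. It costs one covariate. The procedure is in the visit schedule, but the team should confirm that the CRF separates trial laser from earlier laser.
3. For the mechanistic analysis and the acuity-loss safety summary within the implant arm, use the post-laser pre-operative BCDVA as reference. It is already collected.
4. Optional: measure BCDVA in both arms after laser and before randomisation, and use that as baseline. Because it is best-corrected acuity, this means one refracted chart test per participant and the scheduling for it; the protocol shows no assessment visit at that point.
5. Reconcile the three-month criterion in section 8.2.2 with the laser and surgery timings in sections 8.3.1, 8.5 and 10.2.2 and Table 2, including the date at which it is applied. This is a change of wording; the clinical choice belongs to the investigators.
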